6.2 Imaging Process

Cardiac MR imaging will be performed using any 1.5 T scanner with simultaneous ECG recording, according to a protocol for correction of phase offset errors. All images will be obtained using breath-hold in end-expiration. Acquisition will be performed including the following sequences:

- Short-axis cine images of the heart from apex to base, covering the whole LV and RV.
- Body axial cine images of the heart, extending from the surface of the diaphragm to the superior margin of the pulmonary valve.
- Long axis cine images of the heart, extending from the surface of the diaphragm to the superior margin of the pulmonary valve.
- Angiography (flow imaging) will be obtained in the aorta from an imaging plane located perpendicular to the long axis of the ascending aorta, with the plane located just distal to the sino-tubular ridge, and distal also to the origin of the coronary arteries.
- Angiography (flow imaging) will be obtained in the main pulmonary artery from an imaging plane located perpendicular to the long axis of the main pulmonary artery, with the plane located midway between the pulmonary valve and the bifurcation of the pulmonary artery into the branch pulmonary arteries.

- Angiography (flow imaging) will be obtained in each of the branch pulmonary arteries from an imaging plane perpendicular to the long axis of the applicable artery, with the plane located midway between the origin of the artery and the origin of the first branch from that artery.
- Myocardial perfusion imaging during gadolinium infusion will be obtained using short axis views of the heart, as per the baseline cine imaging.
- Delayed imaging after injection of gadolinium will be performed using both short axis and axial views of the heart.

Full details of the procedures can be found in the RESTORE MOP.

6.3 Imaging Analyses

All cardiac MRI images obtained during the RESTORE sub-study will be provided to the Stanford laboratory for interpretation as described in additional detail in the following section. Images will be shipped on digital media (CD/DVD).

All cardiac MRI studies will be analyzed in the same fashion, using commercial software. MRI studies will be analyzed at one time after the conclusion of the study (after last patient last visit).

Studies will be analyzed by one interpreter, either one of the sub-study investigators or personnel trained directly by these investigators. A test set of images will be completed in duplicate and intra-observer variability will be calculated. If this variability is not acceptable (i.e. coefficient of variation < 15%) [171], the interpreter will review interpretation criteria and then repeat the intra-observer variability using the test set (these images will be obtained using the sub-study protocol, but may not include sub-study subjects). The interpreter of images will not have access to treatment assignment nor to the sequence of the studies, but the 2 studies for each subject will be reviewed as a pair.

For interpretation of the MRI, diastole and systole will be assigned manually using the largest and smallest volume of both the RV and LV (this may result in separate assignment of diastole and systole for the 2 ventricles). The diastolic endocardial and epicardial contours of both the RV and LV will be traced manually by one of the study interpreters, and will be processed using software to obtain RV and LV mass, and end-diastolic volume. The chamber volumes will also be manually traced at end-systole, yielding end-systolic volumes. In the LV, papillary muscles will be traced separately, and thus incorporated into the mass rather than volume calculation. Due to difficulties in obtaining consistent tracings with this method in the RV, the RV tracings will exclude papillary muscles. LV and RV volumes/mass will be determined using short axis images. Ejection fraction will be calculated by determining the difference between diastolic and systolic volume for each chamber, and dividing by the diastolic volume of the corresponding chamber. For measurement of flow, the angiography (phase contrast) images will be used, with flow measured in the ascending aorta and main pulmonary artery. For all parameters, the values will be normalized by body surface area (i.e. expressed as indexed values).

For each study, a data collection form will be completed and signed by the study interpreter at the time of the interpretation. This form will be retained at Stanford, with the information entered in an Excel spreadsheet and transferred to the SACCC electronically.

7 Data Management

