Standardized Fick-based pulmonary vascular resistance (PVR_f, in Woods Units) and pulmonary artery capacitance (PAC_f, in mL/mmHg) are calculated as follows:

$$PVR = TPG / CO$$

where TPG = Transpulmonary Gradient (mmHg)
CO = Cardiac Output (L/min)

$$TPG = mPAP - PCWP$$

where mPAP = mean pulmonary artery pressure (mmHg)
PCWP = mean pulmonary capillary wedge pressure (mmHg)

Thus, the Fick-based calculation of PVR is:

$$PVR_f = (mPAP - PCWP) / CO_f$$

where CO_f = Fick cardiac output (L/min)

$$CO_f = VO_2 / ((Ca - Cv) \times cHb \times 13.6)$$

where VO₂ = oxygen consumption according to LaFarge and Meittinen (mL/min)[161]

Ca = arterial oxygen saturation (%) (systemic)
Cv = venous oxygen saturation (%) (pulmonary artery)
cHb = hemoglobin concentration (g/L)

$$VO_2(\text{males}) = (138.1 - 11.49 \ln \text{Age} + 0.378 \text{ HR}) \times \text{BSA}$$

$$VO_2(\text{females}) = (138.1 - 17.04 \ln \text{Age} + 0.378 \text{ HR}) \times \text{BSA}$$

where lnAge = natural log of age in years
HR = heart rate (beats/min)
BSA = body surface area (m²)

The DuBois and DuBois formula is used to calculate body surface area.

$$BSA (m^2) = 0.20247 \times \text{Height}(m)^{0.725} \times \text{Weight}(kg)^{0.425}$$

Pulmonary artery capacitance is calculated as follows.

$$PAC_f = SV_f / PP$$

where SV = stroke volume (mL)
PP = pulse pressure (mmHg)

$$SV_f = CO_f \times 1000 / HR$$

$$PP = \text{systolic PAP} - \text{diastolic PAP}$$

where PAP is the pulmonary artery pressure

15.6 Appendix F: RESTORE Sub-study Protocol**Sub-study Protocol Title: Right Ventricular Response to Rituximab in Systemic Sclerosis-Assoiated Pulmonary Arterial Hypertension – A Magnetic Resonance Imaging Sub-study****Short Title: RESTORE Sub-Study****RESTORE Sub-study Sponsor:****VERA MOULTON WALL CENTER FOR PULMONARY VASCULAR DISEASE,
STANFORD UNIVERSITY****RESTORE Protocol Chair:**

[name]
Stanford University School of Medicine
Division of Pediatric Cardiology
[name]
Palo Alto, CA 94304-5731
[contact]
[contact]
Email: [contact]

RESTORE Protocol Co-Chairs:

[name], FCCP
Stanford University School of Medicine
Vera Moulton Wall Center for Pulmonary
Vascular Disease
Division of Pulmonary & Critical Care Medicine
[name]
Stanford, Ca 94305
[contact]
[contact]
E-mail: [contact]

[name], MPH
Lucile Packard Children's Hospital
Vera Moulton Wall Center for Pulmonary
Vascular Disease
Division of Pediatric Cardiology
[name]
Palo Alto, CA 94304-5731

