4.2 Endpoints

The primary efficacy endpoint will be change in RVEDVI measured by cardiac MRI from baseline to 24 weeks after treatment initiation.

The secondary efficacy endpoints will be as follows:

- Change in RV mass measured by cardiac MRI from baseline to 24 weeks after treatment initiation.
- Change in SV measured by cardiac MRI from baseline to 24 weeks after treatment initiation.

An exploratory endpoint is also defined:

- Cardiac output measured by cardiac MRI

5 Study Objectives

The primary objective of the RESTORE sub-study is to evaluate the therapeutic effect of rituximab on the right ventricle (RV) in patients with SSc-PAH. To achieve this objective, we have developed the following hypotheses:

Primary Hypothesis: Right ventricular end-diastolic volume index, as determined by cardiac MRI, will reduce 24 weeks following rituximab therapy as compared to placebo control, in subjects with SSc-PAH participating in ACE Protocol ASC01.

Secondary Hypotheses:

- Right ventricular mass, as determined by cardiac MRI, will reduce 24 weeks following rituximab therapy as compared to placebo control, in subjects with SSc-PAH participating in ACE Protocol ASC01.
- Stroke volume, as determined by cardiac MRI, will reduce 24 weeks following rituximab therapy as compared to placebo control, in subjects with SSc-PAH participating in ACE Protocol ASC01.

Exploratory Hypotheses:

- Cardiac output, as determined by cardiac MRI, will agree with the main study assessment of cardiac output as well as the standardized Fick-based calculation of cardiac output
- Right ventricular end diastolic volume, as determined by cardiac MRI, will correlate with the standardized Fick-based calculation of pulmonary artery capacitance

6 Treatment of Subjects and Study Measurements**6.1 Subject Clinical Considerations**

Consideration must be given to the need for rate adjustment of intravenous Flolan® during the MRI procedures for those subjects requiring this concomitant background SSc-PAH therapy. Given the requirement for IV extension tubing from the subject to infusion pump while in the MRI scanner, Flolan® flow rate adjustment (increase) will be required to compensate for the longer tubing length to allow for consistent dosing.

Further guidance on this issue may be found in the RESTORE MOP.

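### RESTORE indexes every MRI parameter to body surface area, so MRI cardiac output is not on the L/min scale of the catheter and Fick values it is hypothesised to agree with (minor; exploratory hypothesis only)

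*Protocol*

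**What the plan says.** RESTORE Section 6.3 (Imaging Analyses) describes how chamber volumes and mass are traced, defines ejection fraction as a ratio of volumes, and describes phase-contrast flow, "with flow measured in the ascending aorta and main pulmonary artery". The paragraph then closes with the scaling rule: "For all parameters, the values will be normalized by body surface area (i.e. expressed as indexed values". No parameter is exempted.

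RESTORE Section 4.2 lists as an exploratory endpoint "Cardiac output measured by cardiac MRI". Sections 1 and 5 give the matching hypothesis: "Cardiac output, as determined by cardiac MRI, will agree with the main study assessment of cardiac output", and likewise with the standardized Fick value. A second exploratory hypothesis correlates RV end-diastolic volume with the Fick-based pulmonary artery capacitance (PACf).

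The comparators are not indexed. Protocol Appendix E has "CO = Cardiac Output (L/min" for cardiac output in general and "Fick cardiac output (L/min" for the standardized version. SAP Section 7.3.1 also uses L/min in its PVR formula.

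The secondary endpoints are RV mass and stroke volume, the latter worded "Change in SV measured by cardiac MRI from baseline to 24 weeks after treatment initiation". Neither is given units or named as an index. Only the primary endpoint, RVEDVI, is an index by name.

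**The concern.** An agreement analysis asks whether two methods return the same number for the same patient, so both must be on the same scale. Here one side is divided by body surface area and the other is not. The resulting difference would be systematic and would vary with body size, and it would say nothing about measurement quality. Because it varies between patients, it would shift the mean difference and also widen the spread around it.

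At stake is whether the exploratory cardiac output comparison can be interpreted. The same sentence also leaves the intended scale unclear for stroke volume, RV mass and the RV end-diastolic volume to be correlated with PACf, since these are named without an index.

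**Working it through.** The documents state no figure for this gap, for BSA in this population, or for a limit of agreement, so there is no plan figure to reproduce. The RESTORE power figures in Section 8.2 concern RVEDVI and do not enter.

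**Scales, side by side**
- MRI cardiac output under Section 6.3: L/min divided by BSA, so L/min/m2.
- Main-study cardiac output (Appendix E; SAP 7.3.1): L/min.
- Standardized Fick cardiac output (Appendix E): L/min. Oxygen consumption is multiplied by BSA there, so this is a whole-body value.

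**Size of the gap.** If the true output is CO and both methods are perfect:
- MRI value = CO / BSA; comparator = CO
- relative shortfall = 1 - 1/BSA
- difference = CO x (1/BSA - 1)

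BSA is taken from the Appendix E formula, 0.20247 x height(m)^0.725 x weight(kg)^0.425. Heights, weights and the output of 5.0 L/min are assumptions.

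| Height, weight (assumed) | BSA (m2) | Shortfall | MRI value if CO = 5.0 | Difference |
|---|---|---|---|---|
| 1.50 m, 45 kg | 1.37 | 27.0% | 3.65 | -1.35 |
| 1.60 m, 65 kg | 1.68 | 40.4% | 2.98 | -2.02 |
| 1.80 m, 100 kg | 2.19 | 54.4% | 2.28 | -2.72 |

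At a fixed output the difference doubles from the smallest to the largest of these patients.

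**After correction.** With L/min for all methods, or all outputs divided by the same BSA, the scale gap is 0%.

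**Ejection fraction.** From indexed volumes, (EDV/BSA - ESV/BSA) / (EDV/BSA) = (EDV - ESV)/EDV, because BSA cancels. With EDV 150 mL and ESV 75 mL (assumed) it stays 50% at any BSA. Only dividing the finished ratio by BSA would change it: 50/1.73 = about 29.

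**A separate matter on the Fick side.** Take an assumed woman of 55 years, 1.62 m, 68 kg, heart rate 80, hemoglobin 130 g/L and saturations 95% and 65%. Appendix E gives BSA 1.73 m2 and oxygen consumption 172.7 mL/min. With the printed units (percent, g/L, factor 13.6) output is 172.7 / (30 x 130 x 13.6) = 0.0033 L/min. With saturation as a fraction and hemoglobin in g/dL it is 172.7 / (0.30 x 13 x 13.6) = 3.26 L/min, a factor of 1000. The matching indexed value is 1.89 L/min/m2, 42% lower. The gap against Fick computed above therefore presumes that the Appendix E units are read sensibly.

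**The case against.** The best defence is that Section 6.3 tells the imaging laboratory how to express its readings and does not tell the coordinating center how to compare outputs. The endpoint is called cardiac output, a mismatch of L/min/m2 with L/min would be noticed, and height and weight are collected, so values can be converted back. Imaging detail is also deferred to a RESTORE Manual of Procedures that is not among the documents. This shows that the problem is recoverable and may already be handled elsewhere. It does not remove the conflict, because the protocol sets one scale for the readings and another for the comparators. RESTORE also names neither the BSA formula nor the visit whose height and weight apply, and exact back-conversion needs both.

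Several stronger readings are tempting and are not supported:
- A reader might infer that agreement is bound to be rejected. RESTORE Section 8.3 specifies only ANCOVA for RVEDVI, RV mass and stroke volume. There is no agreement method, limit or rejection rule for the exploratory hypothesis.
- A reader might infer that ejection fraction is corrupted. It is unchanged if computed from indexed volumes, and it is not a RESTORE endpoint.
- A reader might infer that indexing turns stroke volume and RV mass into something other than the endpoints in Section 4.2. That section gives no units, and indexed versions are a coherent choice. Preferring absolute units is a preference.
- A reader might object that weight change over 24 weeks would move the indexed endpoints. That applies equally to RVEDVI, which is rightly an index.
- Correlating an indexed volume with unindexed PACf is not invalid, since correlation does not need shared units. The scale simply has to be stated.

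**Conclusion.** The point holds as a minor inconsistency. The rule in Section 6.3, applied as written, puts MRI cardiac output on a different scale from the two outputs it is hypothesised to match, and no text in the protocol or SAP reconciles them. The artificial shortfall is 1 - 1/BSA, about 27% to 54% over an assumed BSA of 1.37 to 2.19 m2. A single figure such as 40% would be right only for BSA near 1.67 m2, which the documents do not give. The percentage also compares numbers in different units, so it describes what the recorded values would show and is no estimate of measurement error.

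Only an exploratory hypothesis of the sub-study is affected. RVEDVI, its ANCOVA and its power statement are untouched, as is every analysis of the parent trial. The conclusion rests on the protocol and SAP alone; the Manual of Procedures might already contain the needed exception.

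**What to change.** Replace the last sentence of that paragraph in RESTORE Section 6.3 with text that says:
- RV and LV end-diastolic and end-systolic volumes are indexed to BSA, with RVEDVI as the primary endpoint;
- ejection fraction is not indexed;
- cardiac output is compared on one scale for all methods, either L/min for MRI, catheter and Fick, or cardiac index for all three;
- stroke volume, RV mass and the RV end-diastolic volume correlated with PACf are each either absolute or indexed, stated for each one. The choice is the sponsor's.

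It would help to name the BSA formula and the visit supplying height and weight, and to transfer absolute values together with the BSA used. The saturation and hemoglobin units in Appendix E need their own correction before any comparison with the Fick output.

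The cost is a short text edit in the sub-study protocol or its manual. Images are read once, after the last patient's last visit, and the same tracings serve either scale, so no extra imaging or re-reading is needed.

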7.1 Tracking Images and Quality Control Procedures

Clinical sites are responsible for collecting, labeling, tracking, and shipping the images to Stanford University as specified in the RESTORE MOP. The exception is the first cardiac MRI study conducted at each site for this sub-study, which will be sent to the SACCC to forward to Stanford without awaiting protocol completion, to allow a blinded quality control review. After an image is collected for a subject, the clinical site is responsible for entering the subject ID and accession numbers into the web-based tracking system (RhoLAB) operated by the SACCC. The RhoLAB tracking system will notify the Stanford laboratory that a CD/DVD is being shipped. The information supplied to Stanford by the SACCC will contain accession numbers, but not subject ID numbers. The only links between subject ID numbers and accession numbers will be at the clinical site and at the SACCC. These links will allow cardiac MRI results to be linked to clinical outcomes through the SACCC. As CDs/DVDs are received at Stanford, the receiving facility must log into the RhoLAB tracking system and verify that the CDs/DVDs were received and document the condition of the CDs/DVDs at the time of receipt. After analyses are completed at Stanford, the analysis results will be supplied by Stanford to the SACCC electronically using accession numbers as unique identifiers.

Upon arrival at Stanford the images will also be logged and stored in a dedicated, locked file. The actual CD/DVD will be retained at Stanford in the event that re-interpretation is required. In addition, this image may be required for quality control purposes.

The intra-observer variability will be determined at the onset of the sub-study interpretation. This will be accomplished by having the reader interpret a set of 5 studies in duplicate, allowing two weeks between the initial and repeat interpretation. For this purpose, the 2 interpretations will be sent to the SACCC for measurement of the coefficient of variation between the duplicate readings. If this does not meet the standard specified in Section 6.3, *Imaging Analysis*, then the individual will review interpretation criteria and repeat the quality control process.

7.2 Database Management

All data will be maintained in hard copy form at Stanford and transmitted to the SACCC electronically. Upon receipt of such data, the SACCC will store it in a central database on the SACCC network that provides protection of subject confidentiality and allows the cardiac MRI study data to be merged with the clinical data from the ASC01 study.

7.3 Retention of Documents

The Stanford database ensures integrity of the data through multiple levels of password protection and routine backups of all data. All data and subject material will be password

protected on the local database, which will only be accessible to the Protocol Chair and Co-Chairs. All data will be subsequently stored on the SACCC network, which will allow the RESTORE sub-study data to be merged with the clinical data from the ASC01 study.

All study-related documents will be maintained in the core facility for 6 years, or longer if required by the FDA.

8 Statistical Considerations and Analytic Plan

[figure not shown]
8.1 Subject Selection or Allocation

The RESTORE sub-study will include all sites participating in the primary ASC01 study that have the capability to perform the required MRI studies. Enrollment within the RESTORE sub-study will consist of consecutive patients at each site, provided that the patient provides consent for this separate sub-study. With regard to patient treatment assignment, all data will be analyzed on the basis of intention-to-treat, in the identical manner as the parent protocol. Any patient excluded from analysis in the parent protocol will also be excluded from analysis in the RESTORE sub-study.

8.2 Sample Size

The sample size for this sub-study is determined in large part by the size of the parent protocol and budget considerations. With these factors in mind, a sample size of 20 subjects in each arm (40 total subjects) is feasible.

Data from van Wolferen indicate that in subjects with pulmonary hypertension, RVEDVI determined by cardiac MRI was 85 ± 25 ml/m². Assuming that the standard deviation does not change during the sub-study, and that there is a 10% (8.5 ml/m²) mean reduction in right ventricular volume index over the placebo group, one obtains the following relationship between the percent reduction and the expected power:

A mean reduction of 10% would power this sub-study at 27.8%. A recent study of resynchronization therapy for left ventricular failure demonstrated a reduction in left ventricular systolic volume index of approximately 15% of the baseline value; if this level is found, the power would increase to 47.6% [172].

Since the main purpose of the RESTORE sub-study is to get a better understanding of how rituximab affects RVEDVI for subsequent research studies, this level of power will suffice.

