The 6MWD has been the most utilized endpoint in PAH trials, and a 33m improvement from baseline is considered clinically significant [160]. For sample size calculations, we assume a change from baseline of 0m for the placebo arm and 33m for the rituximab arm. An effect size of this magnitude is attainable in a 24 week period, and has been seen in as little as 12 weeks in studies using vasodilators. Assuming a standard deviation of 58m (a best guess based on prior studies) and a 20% drop out rate, ASC01 would be powered at 50% to detect a treatment group difference of 33m for this phase II study. If a significant result is found for this primary efficacy endpoint and no safety signals emerge, this study could provide a definitive conclusion about this treatment. In order to achieve 80% power, the true difference between treatment groups would have to be at least 50m. While other studies evaluating other drugs have seen this magnitude of difference in similar timeframes, we have no data on rituximab to suggest the true difference is at least 50m. Furthermore, rituximab would be interesting as a therapy option if the effect size is as small as 33m.

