3.1 Overall Study Design

The RESTORE sub-study will include all sites participating in the primary ASC01 study that have the capability to perform the required MRI studies. Enrollment within the RESTORE sub-study will consist of consecutive ASC01 study subjects at each site, provided that the subject provides consent for this separate sub-study. This should diminish any unintentional bias in patient selection at each site. Thus, both placebo and rituximab arms will be included in the RESTORE sub-study. Twenty subjects from each arm will be recruited into this sub-study. Each subject will be studied at baseline (i.e. prior to initiation of study drug) and at Week 24, or at time of discontinuation. Subjects in RESTORE will undergo comprehensive cardiac MRI evaluation. Given that the primary comparison is a pre/post match, and that the MRI interpretation is performed by individuals blinded to the treatment assignment, it is not likely to introduce bias if one or more sites cannot participate in the RESTORE sub-study. However, should this be the case, the overall study population will be compared to the sub-population captured at these sites with respect to baseline characteristics. Since the RESTORE sub-study will use the same entry criteria as the parent protocol, there should not be a problem with differential patient selection, with the exception of the additional exclusion criteria specified below that relate to the contra-indications to MRI. While it does not appear likely that these criteria will bias the sub-study population, the data analysis will again compare the baseline characteristics of study subjects for the parent protocol to that of the RESTORE sub-study.

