3.3 Recruitment

Recruitment for this sub-study will be limited to subjects who have consented and elected to participate in the ASC01 clinical protocol. Replacement of subjects in this sub-study will occur in the same manner as the parent protocol. Randomized subjects who withdraw from the trial prior to starting rituximab infusion will be replaced. Subjects who discontinue study treatment or withdraw from the trial after initiating the first treatment may not be replaced.

4 Study Design

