8.3 Statistical Analysis of Study Objectives

The primary aim of this sub-study is a comparison of the change in RVEDVI between the rituximab and the placebo arm of the parent trial, in subjects who have cardiac MRI at baseline and at Week 24, or at time of discontinuation. This comparison will be made using an ANCOVA model with change in RVEDVI as the response and treatment, center, and baseline value as covariates. It is not anticipated that non-parametric tests will be required, but the data distribution will be evaluated and suitable data transformation will be performed as needed. However, based upon experience in other studies using similar outcomes, such is not likely to be required [165, 166]. A p-value of 0.05 will be taken as the threshold for significance. For the secondary outcomes of RV mass and stroke volume, a similar analysis will be performed.

9 Safety Monitoring and Reporting

Monitoring and reporting of any adverse events associated with MRI procedures for this sub-study will be the responsibility of the clinical sites and will be reported to the IND holder using the standard mechanisms implemented as described in Section 7, *Safety Monitoring and Reporting*, of the ASC01 clinical protocol which is incorporated by reference for this sub-study.

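### RESTORE's power figures assume both MRIs from all 20 recruits per arm, although the parent trial plans for 20% drop-out over the same 24 weeks

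*Protocol*

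**What the plan says.** Appendix F, 3.1 makes clear that 20 is a recruited number: "Twenty subjects from each arm will be recruited into this sub-study". The sub-study synopsis counts 80 scans in total, which is 40 subjects times two. Appendix F, 8.2 calls this number feasible given the parent's size and the budget ("a sample size of 20 subjects in each arm (40 total subjects) is feasible"). It takes its variability from a cited study in which "RVEDVI determined by cardiac MRI was 85 ± 25 ml/m²", and supposes that "there is a 10% (8.5 ml/m²) mean reduction in right ventricular volume index over the placebo group". That gives a stated power of 27.8%. For a 15% reduction it says that "if this level is found, the power would increase to 47.6" per cent. The section has no term for missing second scans. It accepts the low power because the aim is to inform later research.

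Appendix F, 8.3 compares change in RVEDVI "in subjects who have cardiac MRI at baseline and at Week 24, or at time of discontinuation", by ANCOVA with treatment, center and baseline value. The significance threshold is 0.05 and sidedness is not given. Appendix F, 3.3 replaces randomized subjects who withdraw before infusion, but adds: "Subjects who discontinue study treatment or withdraw from the trial after initiating the first treatment may not be replaced".

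The parent's Protocol 8.1 sizes its Week 24 comparison differently: "Assuming a standard deviation of 58m (a best guess based on prior studies) and a 20% drop out rate". It reports 50% power for a 33 m difference.

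**The concern.** RESTORE enrols consecutive parent-trial subjects and measures its endpoint at the parent's Week 24 time point. The parent calculation allows for one subject in five being lost by then; the RESTORE calculation allows for none and does not say why. A subject without a second scan cannot contribute a change in RVEDVI, and a treated subject who leaves may not be replaced.

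At stake is the reading of the result. The judgement in 8.2 that the power is good enough rests on two specific figures. If those figures leave out a loss that the protocol expects elsewhere, a null RVEDVI result is less informative than 8.2 implies.

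**Working it through.** **Inputs.** RESTORE: n = 20 per arm, SD 25 ml/m², differences of 8.5 ml/m² (10% of 85) and 0.15 × 85 = 12.75 ml/m² (Appendix F, 8.2); α = 0.05 (8.3). Parent: 30 per arm, SD 58 m, difference 33 m, 20% drop-out (Protocol 8.1); two-sided test (8.3.2.1).

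**Formula.** Two-sample t-test power from the noncentral t distribution with 2n − 2 degrees of freedom and noncentrality λ = δ / (SD × √(2/n)).

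**Step 1: reproduce the printed figures.** With n = 20, SD × √(2/n) = 25 × 0.3162 = 7.906. So λ = 8.5 / 7.906 = 1.075 and 12.75 / 7.906 = 1.613. One-sided at 0.05, power is 27.8% and 47.6%, matching both printed figures to one decimal. Two-sided, it is 18.2% and 34.9%, which does not match. With 16 per arm one-sided it is 24.0% and 40.7%, which does not match either. The printed figures therefore use all 20 recruits per arm, no loss and a one-sided test.

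**Step 2: confirm that the parent applies its drop-out.** 30 × 0.8 = 24 per arm. With 24, λ = 33 / (58 × √(2/24)) = 33 / 16.74 = 1.971, and two-sided power is 48.8% (50.4% by normal approximation). With 30, it is 58.2% (59.6%). The stated 50% fits 24, not 30.

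**Step 3: apply a loss to RESTORE.** 20 × 0.9 = 18 and 20 × 0.8 = 16 per arm. The noncentralities are 1.020 and 1.530 at 18, and 0.962 and 1.443 at 16.

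| Evaluable per arm | One-sided, 10% | One-sided, 15% | Two-sided, 10% | Two-sided, 15% |
|---|---|---|---|---|
| 20 (no loss) | 27.8% | 47.6% | 18.2% | 34.9% |
| 18 (10% loss) | 25.9% | 44.2% | 16.8% | 31.8% |
| 16 (20% loss) | 24.0% | 40.7% | 15.4% | 28.7% |

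At 20% loss the one-sided figures fall by 3.8 and 6.9 points, and the two-sided figures by 2.8 and 6.2 points.

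**Step 4: what the planned ANCOVA could recover.** If the baseline-to-Week-24 correlation is r, the residual SD is 25 × √(1 − r²). A 20% loss is offset when 1 − r² = 0.8, that is r = √0.2 ≈ 0.45. The documents give no r, so these are assumptions. At 16 per arm, one-sided, ignoring degrees of freedom spent on center:

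| Assumed r | 10% reduction | 15% reduction |
|---|---|---|
| 0 | 24.0% | 40.7% |
| 0.3 | 25.5% | 43.4% |
| 0.45 | 27.6% | 47.3% |
| 0.7 | 37.1% | 62.9% |

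**The case against.** A reader might infer that the printed power cannot be delivered. The documents do not support that, for three reasons.

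- The second scan may be taken at discontinuation, so a leaver who is scanned stays in the analysis. Only subjects with no second scan are lost, and no document gives a rate for that. The parent's 20% is a general drop-out rate, not a rate of missing MRIs. With 19 per arm the printed calculation gives 26.9% and 45.9%, falls of only 0.9 and 1.7 points.
- The planned analysis adjusts for baseline, whereas 8.2 uses the unadjusted SD. Step 4 shows that a moderate correlation would bring power back to the printed level even at 16 per arm. Appendix F, 2.1 describes the MRI measures as highly reproducible, which makes a very low correlation less likely.
- A reader might also infer that replacement is barred altogether. It is not: withdrawals before infusion are replaced.

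It can also be said that nothing turns on the difference, since 8.2 already discloses power below 50% and the size was fixed by budget and the parent trial.

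These points limit the claim but do not remove the inconsistency. The parent has its own rescue for leavers: the Early Endpoint Visit (Protocol 6.5.6) repeats the Week 24 procedures, and the walk distance obtained enters the primary model (8.5.5). It still allows 20%. Appendix F, 9.1 names a loss specific to MRI, claustrophobia, although the exclusion criteria in 3.2.2 should screen out some of it. Section 8.2 claims no gain from baseline adjustment, so an unstated correlation cannot justify the figures as printed. The low-power rationale does limit the consequence, and this is a minor point.

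**Conclusion.** The point holds in a limited form. The arithmetic in 8.2 is correct for its inputs; the fault is a planning assumption of complete paired scans that is left unexplained and is out of line with the parent's. On the calculation as printed, the two powers are optimistic by about 2 to 4 points (10% reduction) and 3 to 7 points (15% reduction) for losses of 10% to 20%.

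This rests on SD 25, no gain from baseline adjustment, and a loss in that range. The 20% is an upper-end value, because discontinuation scans will retain some leavers.

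The sidedness of the test is a separate and larger matter. Moving to a two-sided test with no loss already lowers the figures to 18.2% and 34.9%. It matters here only because a restated power has to declare which test it refers to; the omission of losses is present under either test.

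**What to change.** In Appendix F, 8.2, state the expected number of subjects with both MRIs. Use the parent's 20% (20 × 0.8 = 16 per arm) unless a lower loss is justified in the text. Restate both powers on that number and say whether the test is one- or two-sided. At 16 per arm with SD 25 they are 15.4% and 28.7% two-sided, which is in line with the parent's testing, or 24.0% and 40.7% if a one-sided test is declared. If the ANCOVA is expected to recover power, name the correlation assumed.

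The cost is two figures and a sentence or two of text, and a less favourable stated power. Enrolment and the number of planned scans are unchanged.
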